12.1.5 Significance Level for Inferential Analysis

Unless stated otherwise, all statistical tests will be two-sided and conducted at the 5% level, and all quoted confidence intervals will be two-sided 95% confidence intervals.

The primary endpoints will be tested using a multiple testing procedure to preserve the overall alpha level by simultaneously testing the endpoints using a closed procedure with each test performed at an alpha level of 5%. This implies that statistical significance is required for all primary endpoints in order to be able to make confirmatory claims about any of the endpoints.

Further details will be provided in the SAP.

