
Version	Date of Revision	Revision
		
moved into Section 12.6.4.2
 
• In Section 12.3.4, Debriefing of risk of smoking are removed as not included in the SDTM data base. Product preference and Willingness to use the product will be summarized together with Baseline characteristics.• Clarified that the level of CO will serve as compliance tool starting from Day 2, because of possible carry over effect (in Section 12.4)• In Section 12.5, text was adapted to the updated definition of analysis periods (1 to 4). Clarified that summaries for the FAS will be produced only if this set differs from the Safety population by more than 10%• In Section 12.6.1.1:
◦ Title was changed so to reflect that the analyzed endpoints were serving for the evaluation of the primary objectives.◦ Clarified the value to be used in the analysis for repeated measurement on analysis day (e.g. COHb at Day 5)◦ A proc GLM approach will be used for the analysis of THS 2.2 and mCC data. Results will be graphed in a Forest plot• In Section 12.6.1.3, a sensitivity analysis was added for the analysis of Section 12.6.1.1 by means of a mixed model approach without LOCF missing imputation. Clarified that the sensitivity analysis on the compliant population will be produced also for the comparison between THS 2.2 Menthol and SA.• In Section 12.6.2 and 12.6.2.5:
◦ Added summaries for the endpoints of the primary analysis◦ Clarified that the p-value will only be produced at Day 90 conditionally on the statistical significance at Day 5◦ Clarified that the CO breath test will be analyzed in the regular scale◦ Text and list of TFL adjusted according to the general rules for summaries of BoExp◦ Summaries of Nicotine and cotinine concentration not produced as a change from baseline and data will be analyzed on the log space. The mixed model code was removed to analyze results using ANCOVA by timepoint for consistency with other analyses.◦ Clarified that the ratio will be estimated for the analysis of nicotine and cotinine C_{peak} and C_{avg} on Day 5. The median difference will be tabulated for the t_{peak} on Day 5.◦ CYP1A2 and CYP2A6 activity will be analyzed in the log space and the THS 2.2 Menthol:mCC ratio will be presented.◦ Percent change from Baseline will be summarized and listed for the QSU-brief. Data will be analyzed

Version	Date of Revision	Revision

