**Table 13: Coefficients of Variation (ZRHX-EX-01 study)**

	THS 2.2 Menthol/mCC MR (CV)
COHb	0.44 (0.14)
3-HPMA	0.28 (0.20)
MHBMA	0.11 (0.47)
S-PMA	0.07 (0.50)

Abbreviations: 3-HPMA = 3-hydroxypropylmercapturic acid; CC = conventional cigarettes; COHb = carboxyhemoglobin; CV = coefficients of variation; MHBMA = monohydroxybutenyl mercaturic acid; MR = mean ratios; S-PMA = S-phenylmercapturic acid; THS 2.2 = Tobacco Heating System 2.2.

Based on these two sets of assumptions on the mean ratios and coefficients of variations for the four primary BoExp on Day 5, the power to demonstrate a reduction was computed. Subjects are expected not to have any reason for exclusion from the PP Set in the confinement period for THS 2.2 Menthol arm and in ambulatory and confinement condition for the mCC arm.

Fifty percent of the subjects are expected to be excluded from the PP Set in the THS 2.2 Menthol arm in the ambulatory (mostly due to lack of compliance to the randomized product). Thus the expected populations on which the reductions will be assessed as described in Table 14.

Table 14: Sample Size to Assess the Reductions

	Sample size to assess the reduction (THS 2.2 Menthol:mCC)
COHb	80:40
3-HPMA	80:40
MHBMA	80:40
S-PMA	80:40
Total NNAL	40:40

Table 15 describes the expected power to demonstrate a reduction on all 5 primary BoExps in smokers switching from mCC to THS 2.2 Menthol as compared to those continuing to smoke mCC, using one-sided test with 2.5% type I error probability using the assumptions from YVD-CS01-EU and ZRHX-EX-01 given a sample size of 160 smokers (~80 in THS 2.2 Menthol, ~40 in mCC, and ~40 in the SA arm).

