12.6.2.3 Nicotine and Cotinine Pharmacokinetic Parameters

The parameters C_{peak} , C_{avg} and t_{peak} will be calculated on Day 5 as described in Section 7.2 "Pharmacokinetic Parameters". The data will be listed and summarized for both nicotine and cotinine.

The analysis will compare the log-transformed C_{peak} and C_{avg} on Day 5 between the THS 2.2 Menthol and mCC arms. An analysis of variance (ANOVA) model will be used with terms for sex, average daily mCC consumption over the last 4 weeks as reported during screening and randomization arm.

The SAS code will be similar to that described in Section 12.6.1.3 "Sensitivity Analysis", with no baseline value being included in the model.

LS means for each product along with the ratio (THS 2.2 Menthol : mCC) and 95% CI will be presented in the tables.

For t_{peak} on Day 5 the comparison between the THS 2.2 Menthol and mCC arms will be made by the Wilcoxon Rank Sum test using PROC NPAR1WAY in SAS. Median difference and 95% CI using the Hodges-Lehmann estimate will be tabulated.

The following code will be used:

```
Proc npar1way data=_data_ hl median;
  Class randomization_arm;
  Var tpeak;
  Run;
```

All summaries and analyses will be performed on the PP Set and FAS.

The data will be presented in the below outputs:

TFL number	Title
TABLES	
15.2.4.21.1	Descriptive Statistics of Plasma Nicotine and Cotinine PK Parameters on Day 5 – PP Set
15.2.4.21.2	Descriptive Statistics of Plasma Nicotine and Cotinine PK Parameters on Day 5 – FAS
15.2.4.22.1	Analysis of Plasma Nicotine and Cotinine PK Parameters on Day 5 – PP Set
15.2.4.22.2	Analysis of Plasma Nicotine and Cotinine PK Parameters on Day 5 – FAS
LISTINGS	
15.3.3.4	Listing of Nicotine and Cotinine PK Parameters on Day 5

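### The t_peak code in SAP 12.6.2.3 requests the median-scores test, while the text names the Wilcoxon rank-sum test; the tabulated Hodges-Lehmann estimate is unaffected (minor)

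*SAP*

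**What the plan says.** SAP 12.6.2.3 states that for t_peak the "comparison between the THS 2.2 Menthol and mCC arms will be made by the Wilcoxon Rank Sum test using PROC NPAR1WAY in SAS". The next sentence gives the output: "Median difference and 95% CI using the Hodges-Lehmann estimate will be tabulated". The code is then introduced with "The following code will be used", and its PROC statement is "Proc npar1way data=_data_ hl median". It names two options, HL and MEDIAN. There is no WILCOXON option and no EXACT statement. The code serves nicotine and cotinine, each in the PP Set and the FAS (Tables 15.2.4.22.1 and 15.2.4.22.2), so four comparisons.

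Nothing announces a change of test. The revision history (SAP 3.1) says only "The median difference will be tabulated for the" t_peak on Day 5, and SAP section 9 lists no change for this endpoint. Protocol 12.1.5 sets the default: unless stated otherwise, "all statistical tests will be two-sided and conducted at the 5% level".

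**The concern.** The text and the code name different tests. The Wilcoxon test uses the ranks of all peak times. The median test reduces each subject to above or below the pooled median and discards the rest. The Hodges-Lehmann interval is obtained by inverting the Wilcoxon test, so a median-test p-value placed beside it has no reason to agree with it.

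The code is prescribed, not offered as a pattern: elsewhere in the same section the C_peak and C_avg code is described only as similar to another block. A programmer who follows it literally runs the median test; one who follows the text runs Wilcoxon. Left open until after database lock, this allows a choice between two tests that can both be called pre-specified.

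**Working it through.** The plan gives no sample size, power or p-value for t_peak, so there is no figure to reproduce. The first step is to compare text with code; the second is to size the possible disagreement.

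**Text against code.** Test named: Wilcoxon rank-sum. Test requested: median scores. Estimate named: Hodges-Lehmann difference with 95% CI. Estimate requested: HL. The estimate matches and the test does not. This relies on the standard meaning of the two SAS keywords; SAS was not run.

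**Inputs.**
- Arms of 80 and 40: SAP section 8, "given a sample size of 160 smokers (~80 in THS 2.2 Menthol, ~40 in mCC, and ~40 in the SA arm".
- Two-sided 5%: Protocol 12.1.5.
- Draws every 2 hours after first use: Protocol 7.5.1.2.
- A 5-minute window per sample: SAP Table 18.
- t_peak defined on actual time: SAP 5.2, objective 5.
- Shape and spread of t_peak: not in the documents, so assumed and varied.

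**The two criteria at m = 80, n = 40, N = 120.**
- Wilcoxon, no ties: U has mean mn/2 = 1600 and SD √(mn(N+1)/12) = √(3200 × 121/12) = 179.6. It is significant when U is more than 1.96 × 179.6 = 352 from 1600. The Hodges-Lehmann limits are the ordered pairwise differences at about positions 1600 ± 352, so without ties the interval excludes zero when the test rejects.
- Median test: the count S of THS subjects above the pooled median has mean 40 and variance [mn/(N(N−1))] × 30 = (3200/14280) × 30 = 6.72, so SD 2.59. It is significant when |S − 40| exceeds 1.96 × 2.59 = 5.08, that is, when S is at least 46 or at most 34. How far a subject lies from the median does not enter.

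The asymptotic efficiency of the median test relative to Wilcoxon is (2/π)/(3/π) = 2/3 for normal data and 1/3 for uniform data.

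**Simulated power, 2-hour shift, continuous times (Wilcoxon vs median test).**

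| Assumed shape | Power | Gap |
|---|---|---|
| Laplace | 86% vs 80% | 6 points |
| Normal, mean 8 h, SD 3.5 h | 81% vs 58% | 23 points |
| Uniform, 1-15 h | 67% vs 25% | 42 points |

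With 0-5 minute variation the uniform gap is about 44 points. A second set of assumptions gave 86% vs 82% (Laplace, scale 2.8 h), 70% vs 47% (normal, SD 4 h) and 56% vs 21% (uniform, 0-16 h): gaps of 4, 23 and 35 points. On an exact 2-hour grid with Laplace data the median test was slightly ahead (88% vs 85%).

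**Disagreement with the Hodges-Lehmann interval, 2-hour shift.**

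| Times | Median test vs interval | Wilcoxon vs interval |
|---|---|---|
| 0-5 min variation, all distinct (Laplace / normal SD 3.5 h / uniform 1-15 h) | 13% / 25% / 44% | about 0% |
| 0-5 min variation in whole minutes (normal SD 4 h / uniform 0-16 h) | 19% / 25% | 8% / 7% |
| Exact 2-h grid (normal SD 4 h / uniform 0-16 h) | 35% / 15% | 48% / 36% |

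On continuous normal and uniform data nearly every conflict was a non-significant median test beside an interval excluding zero (24.0 of 25.1 points for normal, 35.4 of 35.6 for uniform). On the exact grid the direction mostly reverses: many pairwise differences are exactly zero, so the interval tends to include zero.

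**The case against.** The strongest reply is that this is a one-word slip with little riding on it. The text states the intended test. For t_peak the SAP expressly tabulates only the Hodges-Lehmann difference and CI, and HL is in the code. Where the SAP wants a p-value it says so, as in 12.6.1.1. The table shells are a separate document, so whether a t_peak p-value is printed cannot be seen here. The objective is to describe the PK profiles, outside the success criterion in SAP 5.5.2. All of this stands and sets the severity. It does not remove the inconsistency, because a comparison made by a named test implies a test result and the prescribed code would supply the wrong one.

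The reply also limits three stronger readings that a reader might infer:
- *That the median test always loses power heavily.* The documents give no t_peak distribution. The loss is small for heavy-tailed data and can reverse on an exact grid.
- *That changing the option by itself makes p-value and interval agree.* On an exact 2-hour grid Wilcoxon and the interval still disagreed in 36-48% of trials under one set of assumptions and 45-54% under another, more often than the median test did in the normal and uniform cases tabulated. Agreement needs actual times with few ties.
- *That the sponsor deliberately changed the test.* Neither the revision history nor section 9 says so. MEDIAN may have been added to obtain the median difference, but that is a guess.

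Finally, SAS was not run, so it is unconfirmed that HL alone prints no Wilcoxon result. If it does print one, two tests appear and the code still does not request the named one.

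**Conclusion.** The point holds as a minor inconsistency between text and code: followed literally, the code runs a different test from the one stated. The tabulated Hodges-Lehmann estimate and interval are not affected, and nothing in the documents supports reading this as an error in the reported t_peak difference or as a threat to the primary conclusion.

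The exposure is confined to any p-value taken from the code, in up to four comparisons. Its size is illustrative only: disagreement with the interval in roughly 13-44% of trials at a 2-hour shift with distinct times, and a Wilcoxon power advantage of about 6 to 44 points. These figures assume 80:40, a two-sided 5% level, the chosen shapes and asymptotic tests. The number analysed may be smaller: SAP 7.2 requires every sample to be present, while Protocol 7.5.1.2 accepts that some subjects give fewer than eight samples after first use.

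**What to change.** In SAP 12.6.2.3 replace MEDIAN with WILCOXON and keep HL: `proc npar1way data=_data_ wilcoxon hl alpha=0.05;`. State in SAP 7.2 that t_peak is computed from actual, not nominal, sampling times, in line with the endpoint definition, so that the p-value and the interval agree closely; exact agreement needs untied times. State whether a two-sided p-value is tabulated for t_peak. Arm medians can come from the descriptive Tables 15.2.4.21.1 and 15.2.4.21.2. If the median test was in fact intended, correct the text and list the change in section 9.

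The cost is one line of code and two sentences, with no new data, subjects or tables. It should be settled before database lock.

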12.6.2.4 CYP1A2 Activity

CYP1A2 activity will be measured in plasma on Day 0, Day 5 and Day 90. In this study the CYP1A2 activity will be calculated using the molar ratio of PX and CAF, as described in Section 7.1.3 "CYP1A2". Descriptive statistics of the values and percent change on Days 5 and 90 from Baseline and supportive listings will be provided.

The analysis will compare the log-transformed Day 5 values between the THS 2.2 Menthol and mCC arms and between the THS 2.2 Menthol and SA arms. ANCOVA models will be used on CYP1A2 activity levels with terms for log-transformed baseline, sex, average daily mCC consumption over the last 4 weeks as reported during screening and randomization arm. No adjustment will be made for multiple comparisons. If the results from the Day 5 analysis are significant (one-sided p-value ≤ 0.025) then the statistical significance will be repeated for the analysis at the Day 90 values. The SAS code will be similar to that described in Section 12.6.1.3 "Sensitivity Analysis".

Geometric LS means for each product along with the ratio (THS 2.2 Menthol :mCC) and 95% CI will be presented in the tables.

CYP1A2 activity will also be examined to compare the observed reductions in THS 2.2 Menthol vs. SA using the same methodology as above.

If there are any CYP1A2 assessments performed within 5 half-lives since the use of a concomitant medication affecting CYP1A2 activity, the analysis will be repeated by excluding these assessments for both the PP Set and FAS

All summaries and analyses will be performed on the FAS, and PP Set.

The data will be presented in the below outputs:

TFL number	Title
TABLES	
15.2.4.23.1	Descriptive Statistics of CYP1A2 Activity (%) – PP Set
15.2.4.23.2	Descriptive Statistics of CYP1A2 Activity (%) – FAS

TFL number	Title
15.2.4.24.1	Analysis of CYP1A2 Activity (%) – PP Set
15.2.4.24.2	Analysis of CYP1A2 Activity (%) – FAS
LISTINGS	
15.3.3.5	Listing of CYP1A2 Activity and Changes from Baseline

12.6.2.5 Risk Markers

The risk markers are:

- Systolic and diastolic blood pressure on Day 0, Day 6, Day 30 Visit, Day 60 Visit, and Day 90 Visit.
- hs-CRP, homocysteine, blood glucose, LDL, HDL, TG, and TC in serum on Day 0, Day 30 Visit, Day 60 Visit, and Day 90 Visit.
- Fibrinogen in plasma on Day 0, Day 30 Visit, Day 60 Visit, and Day 90 Visit.
- HbA1c in blood on Day 0 and Day 90 Visit.
- sICAM-1 in serum on Day 0, Day 6, Day 30 Visit, Day 60 Visit, and Day 90 Visit.
- WBC and platelet count in blood on Day 0, Day 6, Day 30 Visit, Day 60 Visit, and Day 90 Visit.
- 8-epi-PGF2 α and 11-DTX-B2 in 24 hour urine on Day 0, Day 5, Day 30 Visit, Day 60 Visit, and Day 90 Visit (expressed as concentration adjusted for creatinine).
- Body weight and waist circumference on Day -2 and Day 90 Visit.

The results along with the changes from baseline will be listed and summarized. In addition line graphs will be produced for product means (and 95% CI) over all timepoints.

The analysis will compare the results on Day 90 between the THS 2.2 Menthol and mCC arms, and between the THS 2.2 Menthol and SA arms for the FAS and PP set. An ANCOVA model will be used with terms for Baseline, sex, average daily mCC consumption over the last 4 weeks as reported during screening and randomization arm. No adjustment will be made for multiple comparisons.

Blood pressure, HbA1c, LDL, HDL, TG, TC, WBC, body weight and waist circumference will be analyzed in the regular scale. 8-epi-PGF2 α , 11-DTX-B2, sICAM will be analyzed in the logarithmic scale. Other risk markers will be logarithmically transformed prior to analysis if there is evidence of non-normality by means of Shapiro-Wilks test.

The SAS code will be the same as described in Section 12.6.1.1 “Analysis of Biomarkers of Exposure for Primary Objectives”.

LS means for each product along with the difference (THS 2.2 Menthol - mCC) or ratio (THS 2.2 Menthol : mCC) and 95% CI will be presented in the tables along with a forest plot of the results.

If there are any 11-DTX-B2 assessments performed within 5 half-lives since the use of a concomitant medication affecting the production of 11-DTX-B2, the analysis will be repeated by excluding these assessments for both the PP Set and FAS

All tables, figures and analyses will be produced for the FAS and PP set. Figures will be produced for the PP Set.

The data will be presented in the below outputs:

TFL number	Title
FIGURES	
15.1.2.3.1	Forest Plot of Statistical Analysis of Risk Markers – PP Set
15.1.2.4.1	Risk Markers Arithmetic Mean and 95% CI for Percent change from baseline – PP Set
15.1.2.4.2	Risk Markers Arithmetic Mean and 95% CI for Percent change from baseline – FAS
TABLES	
15.2.4.25.1	Statistical Analysis of Risk Markers – PP Set
15.2.4.25.2	Statistical Analysis of Risk Markers – FAS
15.2.4.26.1	Descriptive Statistics of Blood Pressure (mmHg) – PP Set
15.2.4.26.2	Descriptive Statistics of Blood Pressure (mmHg) – FAS
15.2.4.27.1	Descriptive Statistics of hs-CRP (units), homocysteine (units), blood glucose (units), LDL (units), HDL (units), TG (units), and TC (units) – PP Set
15.2.4.27.2	Descriptive Statistics of hs-CRP (units), homocysteine (units), blood glucose (units), LDL (units), HDL (units), TG (units), and TC (units) – FAS
15.2.4.28.1	Descriptive Statistics of Fibrinogen (units) – PP Set
15.2.4.28.2	Descriptive Statistics of Fibrinogen (units) – FAS
15.2.4.29.1	Descriptive Statistics of HbA1c (units) – PP Set
15.2.4.29.2	Descriptive Statistics of HbA1c (units) – FAS
15.2.4.30.1	Descriptive Statistics of sICAM (units) – PP Set
15.2.4.30.2	Descriptive Statistics of sICAM (units) – FAS
15.2.4.31.1	Descriptive Statistics of Total WBC Count (units), Neutrophils Counts (units), Basophils Counts (Units), Eosinophils Counts (units), Lymphocytes Counts (units), Monocytes Counts (units) and Platelet Count (units) – PP Set
15.2.4.31.2	Descriptive Statistics of Total Total WBC Count (units), Neutrophils Counts (units), Basophils Counts (Units), Eosinophils Counts (units), Lymphocytes Counts (units), Monocytes Counts (units) and Platelet Count (units) – FAS

TFL number	Title
15.2.4.32.1	Descriptive Statistics of 8-epi-PGF2 α (units) and 11-DTX-B2 (units) – PP Set
15.2.4.32.2	Descriptive Statistics of 8-epi-PGF2 α (units) and 11-DTX-B2 (units) – FAS
15.2.4.33.1	Descriptive Statistics of Body weight (kg) and waist circumference (cm) – PP Set
15.2.4.33.2	Descriptive Statistics of Body weight (kg) and waist circumference (cm) – FAS
LISTINGS	
15.3.3.5	Listing of Risk Markers and Collection Times

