The PP Set will be the primary analysis for BoExp, and risk markers. The full analysis set will be the primary analysis set for compliance to randomization arm. Exposure and questionnaires will be described by randomization arm and according to product use categories (see Table 20).

A sensitivity analysis will be run on the compliant population for the for BoExp and risk markers.

Safety will be analyzed using the safety population and the full safety population by randomization arm and according to the product use categories (see Table 20).

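### A Shapiro-Wilk test on the trial data decides whether five risk markers are reported as a difference or a ratio, so their estimand is not fixed in advance

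*SAP*

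**What the plan says.** SAP 12.6.2.5 (Risk Markers) sorts the markers into three groups.

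- Regular scale: "Blood pressure, HbA1c, LDL, HDL, TG, TC, WBC, body weight and waist circumference will be analyzed in the regular scale".
- Log scale: 8-epi-PGF2α, together with "11-DTX-B2, sICAM will be analyzed in the logarithmic scale".
- Everything else: "Other risk markers will be logarithmically transformed prior to analysis if there is evidence of non-normality by means of Shapiro-Wilks test".

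The Day 90 ANCOVA compares THS 2.2 Menthol with mCC, and also "between the THS 2.2 Menthol and SA arms for the FAS and PP set". Results are tabulated as LS means "along with the difference (THS 2.2 Menthol - mCC) or ratio (THS 2.2 Menthol : mCC) and 95% CI", so the effect measure follows the scale. The two sets have separate inferential tables: 15.2.4.25.1 for the PP Set and 15.2.4.25.2, "Statistical Analysis of Risk Markers – FAS". SAP Section 10 ranks the sets: "The PP Set will be the primary analysis for BoExp, and risk markers".

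Protocol 12.6.4 gives selected risk markers the hypothesis of protocol 12.5.4, which compares geometric means. SAP Section 9 (changes from the protocol) does not mention the normality rule.

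**The concern.** A pre-test on the outcome data chooses the estimand. A mean difference in native units and a ratio of geometric means answer different questions, and for five markers the plan does not commit to either.

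The rule is also incomplete. It does not give a significance level (the protocol's general 5% level may be meant). It does not say whether raw values or model residuals are tested, which timepoint and arms enter, which analysis set is used, or whether one decision applies to both sets and both contrasts. Two programmers could follow it faithfully and report different effect measures for the same marker.

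The FAS and the PP Set are expected to differ a good deal at Day 90. SAP Section 8 expects half of the THS arm to be excluded from the PP Set in the ambulatory period. The FAS table is where a reader checks whether the PP result depends on those exclusions. That check is harder if one table shows a difference and the other a ratio.

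**Working it through.** The plan states no figure for this rule, so there is none to reproduce.

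**1. Markers left to the test.** The SAP 12.6.2.5 list is systolic and diastolic blood pressure, hs-CRP, homocysteine, glucose, LDL, HDL, TG, TC, fibrinogen, HbA1c, sICAM-1, WBC, platelets, 8-epi-PGF2α, 11-DTX-B2, weight and waist. Removing the markers with a named scale leaves hs-CRP, homocysteine, blood glucose, fibrinogen and platelet count.

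**2. Set sizes.** From SAP Section 8, the planned numbers are 80 THS, 40 mCC and 40 SA, and the Day 90 PP expectation is 40 THS and 40 mCC. SA retention is not given, so it is varied.

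- THS and mCC only: FAS 80 + 40 = 120; PP 40 + 40 = 80.
- Three arms, SA fully retained: FAS 160; PP 40 + 40 + 40 = 120.
- Three arms, half of SA retained (assumed): FAS 160; PP 40 + 40 + 20 = 100.

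**3. How often the sets disagree, if each is tested separately.** Values are log-normal with log-SD = √ln(1 + CV²); for example, CV 0.20 gives √ln 1.04 ≈ 0.198. The PP Set is nested in the FAS, exclusions are unrelated to the marker, pooled raw values are tested at 5%, and there are 4,000 runs per cell. No CV for these markers is in the documents, so a range is shown.

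| CV | 120 vs 80 | 160 vs 120 | 160 vs 100 |
|---|---|---|---|
| 0 (normal) | 6.3% | 4.1% | 6.0% |
| 0.10 | 14.3% | 14.0% | 17.4% |
| 0.15 | 20.3% | 19.0% | 25.4% |
| 0.20 | 23.4% | 18.4% | 25.8% |
| 0.25 | 22.3% | 12.7% | 20.1% |
| 0.30 | 16.0% | 6.1% | 12.3% |
| 0.40 | 5.5% | 0.8% | 2.2% |
| 0.50 | 1.3% | 0.0% | 0.2% |

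Repeat simulations of the same kind give about 13-28% over CV 0.10-0.25. For skewed markers most disagreements run one way: the larger FAS rejects normality (ratio) and the smaller PP Set does not (difference).

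**4. Raw values or residuals.** With ANCOVA residuals and an assumed baseline correlation of 0.6, disagreement is 14-21% at CV 0.15, 21-28% at CV 0.20 and 16-26% at CV 0.30. The unstated choice also moves the decision itself. At CV 0.15 a 160-subject FAS goes to the log scale in about 51% of trials on raw values but 33-35% on residuals.

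**5. Does the scale change the answer?** The same log-normal data were analysed by ANCOVA on both scales, at 80:40 and 40:40, with baseline correlation 0.6 and a true effect of zero or 0.44 log-SD. For CV 0.10-0.25 the relative THS-mCC effect differs between scales by a median of 0.1-0.6 percentage points (95th percentile 0.3-1.7). The 5% significance verdict changes in about 1-2% of null trials and 2-6% of non-null trials.

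**The case against.** The strongest reply is that disagreement is common only where it does little harm. At low CV the two scales give nearly the same relative effect (step 5), and a difference divided by the reference LS mean recovers almost the same percentage. At CV 0.50 or above both sets go to the log scale almost always. This stands and limits the severity.

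The SAP does not say that the test is run per set. One decision per marker, used in both tables, is an equally natural reading and gives no FAS/PP disagreement. This also stands, so every rate in step 3 is conditional. It does not rescue the rule, because a single decision still leaves the estimand open until outcome data are tested.

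Comparison on a common scale is partly available already. Percent-change figures (15.1.2.4.1 and 15.1.2.4.2) and paired descriptive tables (15.2.4.27, 15.2.4.28 and 15.2.4.31) exist for both sets. They help, but they are unadjusted and do not replace the ANCOVA estimate.

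The rule is written down in advance, and the study statisticians stay blinded until SAP finalisation or database lock, whichever is later. A reader might infer free choice after unblinding; the documents do not support that.

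A reader might also combine the per-marker rates into a high chance that at least one marker splits. That would need CVs that the documents do not give, independent decisions across markers, and per-set testing. Nor is the choice arbitrary for every mildly skewed marker. On raw values the 160-subject FAS picks the log scale about half the time only near CV 0.15; at CV 0.20 and 0.25 it does so in about 75% and 91% of trials.

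**Conclusion.** The point holds as a minor one. For hs-CRP, homocysteine, blood glucose, fibrinogen and platelet count, the choice between a mean difference and a geometric-mean ratio is left to an underspecified normality test on the trial's own data. That part rests on the text alone.

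The size is conditional. If the test is run separately in the FAS and the PP Set, which the SAP neither states nor excludes, one marker lands on different scales in about 13-28% of trials at CV 0.10-0.25, 6-16% at CV 0.30, and about 1% or less at CV 0.50. These are raw-value figures that assume log-normality, a 5% test level, the set sizes above and exclusions unrelated to the marker.

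The practical effect is modest. The markers are secondary endpoints analysed without multiplicity adjustment. The success criterion rests on five other biomarkers, all fixed on the log scale, so nothing here touches the primary conclusion. What is lost is direct comparability of the main FAS and PP tables, and a fixed estimand in line with protocol 12.6.4 and 12.5.4.

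**What to change.** Delete the Shapiro-Wilk sentence in SAP 12.6.2.5. State that hs-CRP, homocysteine, blood glucose, fibrinogen and platelet count are analysed on the natural-log scale, with THS:mCC and THS:SA ratios and 95% CIs in both the FAS and the PP Set. This follows the geometric-mean hypothesis in the protocol and brings FAS/PP disagreement on scale to zero by construction.

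The cost is one sentence and no new data. The downside is that an effect on a low-CV marker such as glucose or platelets appears as a ratio rather than in native units, and platelets would be on a different scale from WBC in the same panel. The descriptive tables still show native units.

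A weaker alternative is to decide the scale once per marker on blinded pooled data, stating the test level, the input and the timepoint, and to make that decision binding on both sets and both contrasts. This removes the FAS/PP split but still lets the data choose the estimand.
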